The changes in the mean fatigue scores were -0.58, -5.16, and -2.66 for the control, EXER, and COMB groups respectively, from pre-test to immediately post-intervention in the pilot study. The Cohen's d effect sizes for the EXER and COMB groups were 0.51 and 0.23, respectively; whereas the overall effect size was 0.21. As no similar cluster-RCT has been reported in the literature and the cause of general fatigue is heterogeneous, we assumed that an intra-correlation coefficient would be low (0.01) within each cluster (43). Based on an effect size of 0.21 in the pilot study, and four clusters (community centres) per group with an intraclass correlation of 0.01, a significance level (α) of 0.05, and a power ($1-\beta$) of 0.8 for a two-sided test, the sample size was calculated to be 76 participants per group according to NCSS PASS 14. For a long-term follow-up of 12 months, 285 participants (95 per group) will be recruited after considering an attrition rate of 20%. Using computer-generated random numbers, a biostatistician not affiliated with this study will randomize the centres into either: control, EXER, or COMB. The randomization will be stratified based on the size of the centres. Small-medium centres will be defined as those with < 800 ($n=9$) clients, whereas those with > 800 clients will be defined as large ($n=3$). The number of participants recruited in each centre will be in proportion to the size of the centre (i.e., the total number of clients). We estimate that about 25-50% (4, 16, 44) of the 8,710 members of these centres will be eligible to participate. To avoid selection biases, the allocation to the study groups will be concealed from the researchers until the recruitment of the sample and measurement of the baseline have been completed (please refer to the item 13 in this application for details of the collaborators).

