SPSS version 23.0 will be used to analyse the data. An intention-to-treat analysis will be adopted. Descriptive statistics will be generated for the demographic data. Normality assumptions for the variables will be checked. The baseline characteristics of the participants in the three groups will be compared using ANOVA for the continuous variables, a chi-square test for the categorical variables, and the Kruskal-Wallis test for the ordinal variables. Mixed-effects modelling will be used to measure changes in the outcome assessments across the mid-term programme (at week 8) and the three post-tests (1 week, 6 months, and 12 months after the intervention) among the three groups, followed by the Helmert contrasts test (if any results are found to be significant)(60). Another mixed-effects modelling approach will be used to measure the participants' attendance rate in the weekly exercise sessions and their adherence to the home exercise during the programme and the follow-up period between the EXER and the COMB groups. Any pre-test outcome scores, demographic information, data on health conditions, comorbidity index, health service utilization, dosages of exercise recommended by the physiotherapist, and participation in other exercise programmes during the study period, indicating significant differences between groups, will be treated as co-variates as needed. Multiple imputations will be adopted to manage missing data. A p-value of < 0.05 will be considered statistically significant. Content analysis will be used to analyse the interview data⁶¹. All audio-taped interviews will be transcribed into Chinese by the RA and the transcriptions will be checked for accuracy by the PI using QSR NVivo 11. The revised transcripts will be coded independently by two (Chinese-speaking) Co-Is. The research team will then discuss the identified codes and come to an agreement on them, grouping them into main (sub)categories with the support of verbatim data. The (sub)categories will then be condensed and/or re-organized when deemed necessary. The research team will examine them for consistency, reach a consensus about their meaning and structure, and devise a list of finalized categories. A set of (sub)categories with supporting verbatim data will finally be generated to identify the major strengths and limitations of the combined intervention to come up with improvements for its future use.

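### The stated inputs (effect size 0.21, four centres per group, ICC 0.01, 80% power) do not give 76 per group: 76 gives about 74% power, and 80% needs about 90

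*Protocol*

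**What the plan says.** The sample size section of the Protocol reports the pilot results first: "The changes in the mean fatigue scores were -0.58, -5.16, and -2.66 for the control, EXER, and COMB groups respectively", from pre-test to immediately after the intervention. It then gives standardised effects: "The Cohen's d effect sizes for the EXER and COMB groups were 0.51 and 0.23, respectively; whereas the overall effect size was 0.21". The type of the overall effect size is not named.

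The calculation follows: "Based on an effect size of 0.21 in the pilot study, and four clusters (community centres) per group with an intraclass correlation of 0.01", with alpha 0.05, power 0.8 and a two-sided test, and "the sample size was calculated to be 76 participants per group according to NCSS PASS 14". The PASS procedure is not named, and no baseline or within-person correlation is given. The 76 is raised to 95 per group (285 in total) for 20% attrition over 12 months.

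On the analysis, the SAP says: "Mixed-effects modelling will be used to measure changes in the outcome assessments across the mid-term programme (at week 8) and the three post-tests". Pre-test scores are among the variables which, when "indicating significant differences between groups, will be treated as co-variates as needed". Group contrasts come after the main model, "followed by the Helmert contrasts test (if any results are found to be significant". The SAP names no method for the degrees of freedom.

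**The concern.** The 80% power figure is the only stated justification for the number recruited, and the paragraph presents it as the result of the inputs listed beside it. If those inputs give a different answer, the justification fails as written.

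The overall test also decides whether the group contrasts are examined at all. At 74% power the chance of missing the assumed effect is 26%, against the stated 20%. At 59% it is 41%. A null three-group result would be read against a power that the written calculation does not show.

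**Working it through.** **Inputs, all from the Protocol's sample size section:** mean changes -0.58 (control), -5.16 (EXER), -2.66 (COMB); d = 0.51 and 0.23; overall effect size 0.21; 4 centres per group; ICC 0.01; alpha 0.05; power 0.80; 76 per group; attrition 20%.

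**The attrition step reproduces.** 76/(1 - 0.20) = 95 per group; 3 x 95 = 285.

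**What 0.21 is.**
- SD implied by EXER v control: (5.16 - 0.58)/0.51 = 8.98.
- SD implied by COMB v control: (2.66 - 0.58)/0.23 = 9.04. Take 9.0.
- Mean of the three changes: -2.80. Deviations: 2.22, -2.36, 0.14. SD (divisor 3): sqrt((4.93 + 5.57 + 0.02)/3) = 1.872.
- Cohen's f = 1.872/9.0 = 0.208, which rounds to 0.21.

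**Power at 76 per group.** Three-group F test with n per group:
- Design effect DE = 1 + (n/4 - 1) x 0.01. At n = 76 there are 19 per centre, so DE = 1.18.
- Noncentrality = 3 n f²/DE = 3 x 76 x 0.0441/1.18 = 8.52.

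| Degrees of freedom | Power at 76 | n per group for 80% | Recruited per group at 20% attrition | Total |
|---|---|---|---|---|
| Individual level (2, 225 at n = 76) | 0.740 | 90 (0.802; 89 gives 0.799) | 90/0.8 = 112.5, so 113 | 339 |
| Centre level (2, 9): 12 centres - 3 arms | 0.588 | 139 (0.801) | 139/0.8 = 173.75, so 174 | 522 |

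The plan states 0.80, 76, 95 and 285. Both rows assume equal centre sizes. In whole, equal centres the requirements become 4 x 23 = 92 and 4 x 35 = 140.

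**Rounding does not explain the gap.** For f from 0.205 to 0.215, power at 76 is 0.72 to 0.76 (individual df) or 0.57 to 0.61 (9 df).

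**Other readings** (individual-level df).
- 0.21 as Cohen's d, two groups, clustered: power 0.22 at 76.
- d = 0.51, two groups, clustered: 72 (4 x 18) already gives 0.802, so this does not lead to 76.
- f = 0.208 with no clustering: 76 gives 0.804 and 75 gives 0.799. This reproduces 76 but drops the stated ICC.
- d = 0.50, two groups, clustered: 4 x 19 gives 0.805 and 4 x 18 gives 0.787. This also reproduces 76 but is not the stated effect size.

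The last two both reach 76 and both depart from the stated inputs, so the documents do not show which calculation was run.

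**What would restore 80% at 76.** The outcome variance would have to fall to 0.873 of its value (individual df) or 0.622 (9 df). The documents do not say whether 9.0 is a raw-score or a change-score SD.
- Raw score: adjustment multiplies the variance by 1 - r², so r must be at least sqrt(1 - 0.873) = 0.36, or sqrt(1 - 0.622) = 0.61.
- Change score: moving to baseline adjustment multiplies the variance by (1 + r)/2, so r must be at most 0.75, or 0.24.

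**Effect detectable with 80% power at 76, unadjusted:** f = 0.225 (individual df) or 0.266 (9 df).

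**The case against.** The strongest reply is that the modelled test is not the planned one. The Protocol compares every follow-up with baseline, and the SAP fits a mixed model over four post-baseline assessments. Either feature can raise power, and with individual df the baseline correlation needed is modest. This stands as far as it goes: 74% is the power of an unadjusted test at one time point, not a ceiling. It does not rescue the paragraph, because no correlation is stated in either document, the calculation does not use one, and the SAP brings in pre-test scores only when groups differ significantly.

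Second, the 20% attrition is for 12 months, while the pilot effect was measured just after the intervention. With all 95 per group still evaluable then, power would be 0.82 (individual df). That softens the practical consequence at the immediate post-test, but the sentence ties 80% to 76.

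Third, neither document specifies centre-level df. This is correct: the 9-df figures are an alternative that applies if that method is used, and they appear here because the method is not named.

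Fourth, the gap between 74% and 80% is modest for an effect taken from a pilot and an assumed ICC. That bears on how much to worry about the trial, not on whether the stated figure follows from its inputs.

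**Conclusion.** The concern holds. No reading of the stated inputs gives 76 per group at 80% power. With 0.21 as Cohen's f, which the pilot figures support, 76 evaluable participants per group give about 74% power and 80% needs about 90; with centre-level df the figures are about 59% and 139. These results rest on equal centre sizes, an ICC of 0.01, and an unadjusted three-group comparison at one time point. Power could be higher under a baseline-adjusted or repeated-measures analysis with a suitable correlation, but the plan states none. The paragraph must be corrected; the planned number of participants need not change.

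**What to change.** Keep 285 participants and restate the paragraph.

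1. Say that 0.21 is Cohen's f for the three-group comparison.
2. Name the PASS procedure with all its inputs, and the df method. Name the same df method in the SAP.
3. If 80% rests on baseline adjustment or repeated measures, state the assumed correlation and whether the SD is of raw or change scores, and make the SAP's use of the pre-test score match.
4. Otherwise replace the 80% statement with wording such as: *76 evaluable participants per group (4 centres x 19, ICC 0.01) give about 74% power for f = 0.21 in an unadjusted three-group comparison at one time point (about 59% with centre-level df); the effect detectable with 80% power is f = 0.225 (0.27 with centre-level df).*

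Optionally, and only as information because the plan claims no pairwise power, add the power on the pilot effects with SD 9.0 (individual df / 9 df): control v the mean of the two exercise arms, d = 3.33/9.0 = 0.37, 0.68 / 0.58; EXER v COMB, d = 2.50/9.0 = 0.28, 0.35 / 0.29; COMB v control, d = 0.23, 0.25 / 0.22.

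The cost is one reworded paragraph and a phrase in the SAP (slightly more if item 3 applies). Under item 4 the stated power is less favourable. Recruitment does not change.

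### Centre size stratifies the randomisation but is absent from the planned models; once centre is fitted as a random effect, this costs power if change differs between large and smaller centres

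*Protocol*

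**What the plan says.** The Protocol, under sample size estimation and random allocation, says "The randomization will be stratified based on the size of the centres". It continues: "Small-medium centres will be defined as those with < 800 ($n=9$) clients"; the three centres above 800 clients are large. The sample size rests on "four clusters (community centres) per group with an intraclass correlation of 0.01". Three arms of four centres, stratified 9 and 3, imply three small-medium centres and one large centre per arm.

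The SAP's analysis text says "Mixed-effects modelling will be used to measure changes in the outcome assessments" over week 8 and the three post-tests. A second mixed-effects model compares attendance and home-exercise adherence between EXER and COMB. Possible covariates are pre-test scores, demographics, health conditions, comorbidity, service use, prescribed exercise dosage and other exercise programmes, and they enter only where they differ significantly between groups. Centre size is not listed. No random effect for centre is named either.

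**The concern.** Stratification takes the difference between large and small-medium centres out of the arm comparison. The analysis benefits only if the model also takes that difference out of the error term. The covariate rule cannot do this: size is not on the list, and a test for imbalance would not pick out a factor balanced by design.

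With four centres per arm, a valid test of the arms depends on the between-centre variance. If change in fatigue differs between large and small-medium centres and size is left out, that difference is counted as unexplained centre variation. The estimated standard error then exceeds the true one, the intervals are too wide, and the stratification yields less than it could.

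**Working it through.** **Plan's own figures.** The documents give no figure for the effect of the stratum. The attrition step reproduces: 76/0.8 = 95 per arm, and 3 × 95 = 285. The 76 itself is approached only by reading 0.21 as Cohen's f in a three-group F test without clustering (74 per group). That is a separate question, and nothing below depends on it.

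**Inputs from the Protocol.** Four centres per arm (one large, three small-medium); 76/4 = 19 evaluable per centre on average; ICC 0.01; two-sided alpha 0.05; d = 0.51, the pilot value for EXER.

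**Assumptions.** Equal centres of 19; total SD 1 for the analysed change; the ICC of 0.01 applies to that change; a shift s (in SD) between large and small-medium centres, which the documents do not give.

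**Formulas, centre-level test.** Let V = between-centre variance within stratum + 0.99/19.
- True SE of an arm difference: √(V/2).
- Expected SE with size omitted: √((V + 0.25s²)/2). The 0.25 is 3 × 0.75/9: the sum of squares of the size indicator within three arms, over 9 df.
- Variance between centres due to size: (1/4)(3/4)s² = 0.1875s².

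**A. Total ICC held at 0.01.** If size explains all of it, s = √(0.01/0.1875) = 0.23 and V = 0.0521. The SE with size is √(0.0521/2) = 0.161; without it, √((0.0521 + 0.0133)/2) = 0.181. Power and type I error are from 100,000 simulated trials, on 9 df without size and 8 with it:

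| Share of ICC due to size | s | SE without / with size | Power without / with size | Change | Type I error without size |
|---|---|---|---|---|---|
| All | 0.23 | 0.181 / 0.161 | 72.5% / 79.1% | +6.6 | 3.1% |
| Half | 0.16 | 0.179 / 0.169 | 73.0% / 75.3% | +2.3 | 4.1% |
| None | 0 | 0.176 / 0.176 | 73.3% / 71.9% | -1.4 | 5.1% |

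**B. Shift added on top of a within-stratum ICC of 0.01.** V = 0.01 + 0.0521 = 0.0621, so the true SE is 0.176. Total ICC = (0.01 + 0.1875s²)/(1 + 0.1875s²).

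| s | Implied total ICC | Expected SE without size | Power without size | Power with size |
|---|---|---|---|---|
| 0.2 | 0.017 | 0.190 | 67% | 72% |
| 0.3 | 0.026 | 0.206 | 61% | 72% |
| 0.4 | 0.039 | 0.226 | 52% | 72% |

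Type I error without size is about 3.8%, 2.5% and 1.6% in these rows.

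**C. No centre effect fitted.** The model SE is about √(2/76) = 0.162 against a true 0.176. The actual two-sided error is about 2Φ(-1.96 × 0.162/0.176) = 7%. Adding size leaves the SE at 0.162 and the error at about 7%.

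**D. Cost when size is irrelevant.** Three-arm models: 12 - 3 = 9 df, falling to 8, and power 73.3% to 71.9%. Adherence model: 8 - 2 = 6 df, falling to 5, and power 67.5% to 64.2% at the same d = 0.51. The Protocol states no effect size for adherence.

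**The case against.** A reader might infer that the planned standard errors are simply too large. The documents do not support that. The SAP names mixed-effects modelling without saying which random effects, and for repeated measures it could mean a participant effect only. In that case (C above) the error runs the other way and the stratum does not repair it. This objection stands, and it is why the point is conditional on a centre effect. The Protocol calls the trial a cluster-RCT and allows for an ICC, so a centre effect is what the design needs, but it has to be written down.

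A reader might also take 52% against 72% as the expected loss. That row needs a total ICC of about 0.039, nearly four times the planned 0.01. The pilot figures imply an SD near 9 points ((5.16 - 0.58)/0.51, if d is the difference in change over the SD). On that scale 0.4 SD is 3.6 points, more than the pilot COMB-control difference of 2.66 - 0.58 = 2.08. Nothing in the documents points to a size effect that large, and the Protocol describes the centres as similar in services and regulation.

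The shift must also be in change. A stable difference in level, present at baseline, largely cancels in the comparison over time. That argument does not reach session attendance, which has no pre-programme value.

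Finally, the Protocol recruits in proportion to centre size, so equal centres of 19 are a simplification. With an assumed 29 per large and 16 per small-medium centre (29 + 3 × 16 = 77 per arm), power without size in the three rows of B is about 67%, 59% and 49%. The direction holds; the percentages are illustrative.

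**Conclusion.** The omission is real: the only stratification factor is missing from the models, and the covariate rule would not bring it in. Two conditions are needed for it to inflate standard errors: centre is fitted as a random effect, and change in the outcome differs by centre size. At the Protocol's ICC of 0.01, leaving size out then makes the SE at most about 12% too large (0.181/0.161) and costs at most about 7 points of power for d = 0.51. The cost is about 2 points if size explains half the clustering, and there is a gain of about 1 point if it explains none. Larger losses require more clustering than was planned for.

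The error is conservative and the estimate stays unbiased, so this is lost efficiency and incomplete prespecification. It does not threaten validity. The unnamed centre effect is the more serious gap, and both should be settled together. The size shift, equal centres and unit SD are assumptions.

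**What to change.** Add to the SAP's analysis text: every outcome model, and the EXER v COMB adherence model, will include centre as a random effect with small-sample degrees of freedom, and the randomisation stratum (small-medium v large) as a fixed effect whatever its significance and whatever the baseline comparisons show. The two terms belong together, because the stratum alone leaves type I error at about 7%.

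The cost is one or two sentences and one centre-level degree of freedom. If size proves irrelevant, that is about 1 point of power in the three-arm models and about 3 in the adherence model. No change to the randomisation, recruitment or data collection is needed.

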Procedures: (*Appendix IV*: Detailed Ethical Considerations; *Appendix V*: CONSORT diagram of the Cluster RCT) Ethical and access approval will be obtained from the Ethics Review Committee of The University and study venues, respectively. Potential participants will be referred to the research team by the collaborators. An RA will screen all potential participants for their eligibility to participate in this study. Written informed consent will then be obtained from all of the participants, to whom all aspects of the study will be explained and questions answered. They will then be interviewed to obtain their health-socio-demographic data, and baseline assessment. After that, the twelve community centres will be randomized to either the control, EXER, or COBM group. Participants from each centre will be placed into their centre's corresponding group to avoid 'contamination' effects across participants. At the mid-term programme, 1 week, 6 months, and 12 months post-intervention, an independent assessor who is blinded to the group allocations will assess the participants' outcomes, which will be compared with the baseline assessment. Focus group interviews will be conducted by the trained RA after the first post-test 1 (one-week post-intervention). Purposive samples of 30 participants from the COMB group will be selected to take part in one interview (4-6 per group). They will be asked to comment on their experiences and (dis)satisfaction regarding the programme, perceptions of its positive/negative aspects, concerns and difficulties in participating and adhering to the programme, and ways of improving the intervention. A semi-structured interview guide will be developed for these interviews, which will be conducted in Cantonese, and all interviews will be audio-recorded for content analysis. Examples of interview questions include: "What are your opinions and comments on your participation in the programme?" and "What are your changes and / or difficulties in adherence to the exercise regimen during and after the 16-week programme?"

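### Recruiting in proportion to centre size before centres are allocated does not assure the stated 95 per group, and the sample size makes no stated allowance for unequal centres or arms (minor)

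*Protocol*

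**What the plan says.** The Protocol section on sample size, recruitment, random allocation and concealment assumes "four clusters (community centres) per group with an intraclass correlation of 0.01". It reports that "the sample size was calculated to be 76 participants per group according to NCSS PASS 14" and that "285 participants (95 per group) will be recruited after considering an attrition rate of 20" per cent. Randomisation is stratified by centre size: nine centres below 800 clients and three above, 8,710 members in all. On quotas it says: "The number of participants recruited in each centre will be in proportion to the size of the centre".

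Allocation is concealed until recruitment and baseline are finished. The Procedures section confirms the order; following the baseline assessment it says: "After that, the twelve community centres will be randomized to either the control, EXER, or COBM group".

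Neither document lists the 12 centre sizes (the protocol points to an application item that is not included), ties centre quotas to 95 per arm, constrains the allocation on total clients, or gives a cluster-size coefficient of variation (CV).

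**The concern.** Quotas are filled before anyone knows which centres will share an arm. The total of 285 can be controlled, but its split into three arms is decided by the later draw of centres. An arm that comes out small cannot be topped up afterwards without recruiting people whose allocation is already known, which the concealment rule is meant to prevent.

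The figure of 95 is also relied on elsewhere: the focus-group sample of 30, given as 31.5% of the COMB group, implies about 95 in that arm (30/0.315 = 95.2). At stake are a stated group size that the design leaves to chance, and a power figure that takes no account of unequal centres or arms.

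**Working it through.** **1. The plan's own figure.** 76/(1 − 0.20) = 95, and 3 × 95 = 285. Both reproduce exactly. Since the total is fixed at 285, any arm above 95 forces another below 95, and at 20% attrition that arm falls below 76. This step needs no assumed centre sizes.

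**2. Equal clusters are ruled out.** The sampling fraction is 285/8,710 = 3.27%. A centre with more than 800 clients recruits more than 800 × 285/8,710 = 26.2. The three large centres together take more than 78.5, so the nine others average less than (285 − 78.5)/9 = 22.9. Equal clusters would be 285/12 = 23.75.

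**3. What equal arms would need.** Each arm's four centres would have to hold about 8,710/3 = 2,903 clients. With nine small-medium and three large centres and four per arm, stratification implies three small-medium plus one large per arm. That narrows the spread of arm totals but does not equalise them.

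**4. Size of the imbalance.** Centre sizes are an assumption, so a range is shown. Sizes were drawn uniformly within each band, keeping draws with a total near 8,710; 285 were recruited in proportion; and three small-medium plus one large centre were randomised to each arm. Evaluable numbers are 0.8 times the unrounded median.

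Power is from a three-group noncentral F test with the protocol's pilot mean changes (−0.58, −5.16, −2.66), ICC 0.01 and an assumed SD of 9:

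- Squared deviations from the mean of −2.80 sum to 4.93 + 5.57 + 0.02 = 10.52, so f = √(10.52/3)/9 = 0.208, close to the protocol's 0.21.
- Information per arm = Σ m/(1 + (m − 1) × 0.01) over its four centres, m being evaluable participants per centre.
- Equal clusters: m = 76/4 = 19, design effect 1 + 18 × 0.01 = 1.18, information 76/1.18 = 64.4, noncentrality 64.4 × 10.52/81 = 8.36, power 0.73.

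| Small-medium / large clients (assumed) | Smallest arm recruited, median | Evaluable, median | Some arm below 90 | Centre-size CV | Mean power (5th, 95th percentile) |
|---|---|---|---|---|---|
| 550-750 / 820-1,050 | 92 | 73 | 19% | 0.19 | 0.73 (0.72, 0.74) |
| 500-799 / 801-1,200 | 90 | 72 | 49% | 0.24 | 0.73 (0.71, 0.74) |
| 400-799 / 801-1,500 | 87 | 70 | 73% | 0.36 | 0.72 (0.70, 0.75) |
| 300-799 / 801-1,800 | 85 | 68 | 85% | 0.50 | 0.71 (0.68, 0.75) |

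Some arm rounds below 95 in 98-99.8% of allocations in every row. The mean power loss against equal clusters is about 0.2 to 1.8 points. At CV 0.50 the design effect rises from 1.18 to 1 + ((1 + 0.25) × 19 − 1) × 0.01 = 1.23.

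**The case against.** The strongest reply is that nothing here is contradictory and little is lost. Under proportional recruitment 95 is the expected arm size, the total stays at 285 (228 evaluable), and arms of 95 arise whenever client totals happen to match. The protocol never promises equal clusters; it openly plans unequal ones, and a common size is at most implicit in a calculation using one n and four clusters per group. Proportional recruitment is also a legitimate choice, giving one sampling fraction across centres. Unequal arms do not always cost power: the 95th percentile (0.74-0.75) exceeds the equal-cluster 0.73, because some allocations put more people in the arms that carry most of the contrast.

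All of this stands, and it limits the point to a minor one. It does not supply a rule that makes 95 per group hold, or an allowance for unequal centres in the stated size.

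A reader might go further and infer that the design cannot deliver 95, or that the smallest arm will probably fall well below 76 evaluable. The documents do not support either. The first ignores that equal totals are possible. The second needs centre sizes that the documents do not give; among the spreads tried, only the widest reaches a median of 68, and the narrower ones leave the arm about 3 to 6 short.

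**Conclusion.** The point holds as a minor one. The stated 95 per group is an expectation with no margin, arm totals are left to the draw of centres, and clusters must be unequal without any stated allowance. The absence of a guarantee and the inequality of clusters follow from the documents alone. The size of the effect rests on assumed centre sizes and, for power, on an assumed SD of 9: a smallest arm typically about 3 to 8 evaluable below 76, and a mean power loss of under 2 points (about 5 at the 5th percentile for the widest spread).

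It would be wrong to blame this feature for power of 0.73 rather than 0.80. In the same calculation 76 per group gives 0.80 with no clustering and 0.73 with equal clusters at ICC 0.01, so that gap exists before any imbalance and should be handled separately.

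**What to change.** Before recruitment starts, set quotas per centre that give every arm the same total under any stratified allocation. Two options:

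- **Equal quotas within stratum**, for example 22 per small-medium and 29 per large centre. Each arm then has 3 × 22 + 29 = 95, and the total is 9 × 22 + 3 × 29 = 285. Cluster-size CV drops to about 0.13 (mean 23.75; SD √[(9 × 1.75² + 3 × 5.25²)/12] = 3.03).
- **About 24 in every centre**: 96 per arm with equal clusters, and 12 × 24 = 288 in total, three more than planned.

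The cost is a short protocol edit. Recruitment is no longer strictly proportional, and the smallest centres give a larger share of members: at an assumed 300 clients, 22 is 7.3% and 24 is 8%, against 3.27% overall. Both are well under the 25-50% the protocol expects to be eligible. The arm totals hold only if centres meet their quotas.

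If proportional recruitment is kept, either constrain the randomisation on total clients per arm (there are 1,680 × 6 = 10,080 stratified allocations to choose from), or restate the size as 285 in total with the expected range of arm sizes. In the latter case, recompute power from the 12 actual centre sizes and state their CV.
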